7.1.6 Withdrawal of consent

Patients may voluntarily withdraw consent to participate in the study for any reason at any time. Withdrawal of consent occurs only when a patient:

- Does not want to participate in the study anymore, and
- Does not allow further collection of personal data.

In this situation, the investigator should make a reasonable effort (e.g. telephone, e-mail, letter) to understand the primary reason for the patient's decision to withdraw his/her consent and record this information.

Study treatment must be discontinued and no further assessments conducted, and the data that would have been collected at subsequent visits will be considered missing. Further attempts to contact the patient are not allowed unless safety findings require communicating or follow-up.

All efforts should be made to complete the assessments prior to study withdrawal. A final evaluation at the time of the patient's study withdrawal should be made as detailed in the assessment table. Novartis will continue to keep and use collected study information (including

any data resulting from the analysis of a patient's samples until their time of withdrawal) according to applicable law.

7.1.7 Follow up for safety evaluations

All patients who complete the Core Phase of the study but do not transition to the Extension Phase must have safety evaluations completed within 30 days after the last dose of study treatment (ribociclib + letrozole + either goserelin or leuprolide). Patients who continue to the Extension Phase will complete safety evaluations within 30 days after the last dose of study treatment of the Extension Phase.

Data collected should be added to the Adverse Events eCRF and the Concomitant Medications eCRF.

7.1.8 Lost to follow-up

For patients whose status is unclear because they fail to appear for study visits without stating an intention to withdraw consent, the investigator should show "due diligence" by contacting the patient, family or family physician as agreed in the informed consent and by documenting in the source documents steps taken to contact the patient, e.g. dates of telephone calls, registered letters, etc. A patient should not be considered lost to follow-up until due diligence has been completed. Patients lost to follow up should be recorded as such on the appropriate Disposition eCRF.

7.2 Assessment types

7.2.1 Efficacy assessments

Efficacy assessments

Tumor response will be assessed locally according to the Novartis guideline version 3.2 (Appendix 14.3) based on RECIST 1.1 (Eisenhauer et al 2009). The imaging assessment collection plan is presented in Table 7-3. There will be no central review of imaging assessments.

Procedure	Screening: day-28 to day 1	Treatment phase*	End of treatment*
CT or MRI (Chest, Abdomen, Pelvis)	Mandated	Recommend every 12 weeks or at different intervals according to local standards of care during treatment phase	Mandated
Brain CT or MRI	Only if suspected brain metastases	As clinically indicated	As clinically indicated
Whole body bone scan**	Mandated	As clinically indicated	As clinically indicated
Bone X-ray, CT or MRI	Only if skeletal abnormalities identified by whole body bone scan (or skeletal survey) at screening, which are not visible in the chest, abdomen, pelvis CT/MRI.	If bone lesion at screening, recommend every 12 weeks or at different intervals according to local standards of care during treatment phase	Mandated only if bone lesion at screening

 Table 7-3
 Imaging Assessment Collection Guidance

Procedure	Screening: day-28 to day 1	Treatment phase*	End of treatment*						
Skin visual inspection and measurement	Only if skin lesions at screening	Recommend every 12 weeks or at different intervals according to local standards of care during treatment phase	Mandated if skin lesions at screening						
CT or MRI of any disease outside of chest, abdomen and pelvis (e.g., neck)	Only if suspected lesion at screening	If lesion identified at baseline, recommend 12 weeks or at different intervals according to local standards of care during treatment phase	Mandated if lesion at screening						
*Tumor evaluation at EOT is required for patients who discontinue study treatment before the first scheduled post-baseline tumor assessment (week 12) and for patients whose previous tumor assessment did not demonstrate PD and was done more than 28 days prior to end of treatment visit. ** Whole body bone scan according to institutional guidelines (e.g. Tc-99 bone scan, whole body bone MRI,									

sodium fluoride positron emission tomography (NaF PET) or fluorodeoxyglucose (FDG) PET).

Baseline/Screening imaging assessments

Imaging assessments will be performed at screening/baseline within 28 days of start of treatment (Day -28 to Day -1 prior to Cycle 1 Day 1).

Any imaging assessments already completed during the regular work-up of the patient within 28 days prior to start of treatment, including before signing the main study ICF, can be considered as the baseline images for this study. Any imaging assessments obtained after study treatment cannot be considered baseline images. The following assessments are required at screening/baseline:

- Chest, abdomen and pelvis CT or MRI
- Brain CT or MRI, if clinically indicated
- Whole body bone scan
- Localized bone CT, MRI or x-ray, for any lesions identified on the whole body bone scan that are not visible on the chest, abdomen and pelvis CT or MRI
- Skin visual inspection and measurement (only if skin lesions at screening)
- CT or MRI of other metastatic sites (e.g. neck), if clinically indicated

If a patient is known to have a contraindication to CT intravenous (IV) contrast media or develops a contraindication during the trial, a non-contrast CT of the chest (MRI is not recommended due to respiratory artifacts, however if CT is not feasible per local regulations, MRI can be performed instead) plus a contrast-enhanced MRI (if possible) of the abdomen and pelvis should be performed.

If brain metastases are suspected at baseline, brain MRI or CT should be completed. Contrast enhanced brain MRI is preferred, however, if MRI contrast is contraindicated, then MRI without contrast or CT with/without contrast is acceptable.

A whole body bone scan should be performed per institutional standard of care [e.g., Tc-99 bone scan, whole body bone MRI, Fluorodeoxyglucose positron emission tomography (FDG-PET) or sodium fluoride (NaF) PET]. Localized CT, MRI or X-rays should be acquired for all skeletal lesions identified on the screening whole body bone scan, which are not visible on the chest, abdomen and pelvis CT/MRI.

If clinically indicated, CT or MRI of other areas (e.g., neck) of disease as appropriate should be performed.

If skin lesions are present at screening, lesion will be measured and visually monitored.

Any potentially measurable lesion that has been previously treated with radiotherapy should be considered as a non-measurable lesion. However, if a lesion previously treated with radiotherapy has clearly progressed since the radiotherapy, it can be considered as a measurable lesion.

Chest x-rays and ultrasound should not be used to measure tumor lesions.

Post-baseline imaging assessments

Imaging assessments as described in Table 7-3 should be performed at the timepoints specified using the same imaging modality used at baseline, irrespective of study treatment interruption or actual dosing (see Table 7-1). Imaging assessments for response evaluation will be performed in recommended timeframe of every 12 weeks or at different intervals according to the local standard of care after screening/baseline, until disease progression, death, lost to follow-up or withdrawal of consent. Imaging assessments should be scheduled using the first dose date as the reference date (not the date of the previous tumor assessment), and should be respected regardless of whether treatment with study treatment is temporarily withheld or unscheduled assessments performed.

Additional imaging assessments may be performed at any time during the study at the investigator's discretion to support the efficacy evaluations for a subject, as necessary. Clinical suspicion of disease progression at any time requires a physical examination and imaging assessments to be performed promptly rather than waiting for the next scheduled imaging assessment.

Each lesion that is measured at baseline must be measured by the same method (either same imaging method or by visual inspection and measurement and when possible, the same local radiologist/physician throughout the study so that the comparison is consistent. If an off-schedule imaging assessment is performed because progression is suspected, subsequent imaging assessments should be performed in accordance with the original imaging schedule.

Combined PET/CT may be used only if the CT is of similar diagnostic quality as a CT performed without PET, including the utilization of IV contrast media. At the discretion of the Investigators, FDG-PET scans may be performed to document progressive disease per RECIST 1.1 (Appendix 14.3).

Confirmation of Clinical Benefit

During the Extension Phase, at every 3 months visit the investigator is required to confirm that the patient continues to receive clinical benefit and may continue receiving study treatment.

7.2.2 Safety and tolerability assessments

Safety will be monitored by assessing physical exam, vital signs, hematological and chemistry labs as well as collecting of the adverse events at every visit during Core Phase (Table 7-1). For patients who continue study participation during Extension Phase, (S)AEs and related

assessments and, pregnancy test will be performed (Table 7-2). For details on AE collection and reporting, refer to Section 8.

Premenopausal women must complete the following pregnancy tests:

- Screening Serum pregnancy test done locally
- Every 4 weeks during treatment urine pregnancy test. Can be administered at patient's home
- End of Treatment visit serum pregnancy test done locally

Premenopausal women who administer urine pregnancy testing at home should complete a simple diary with the dates and the outcome of the urine pregnancy tests while on study treatment. In case of a positive pregnancy test, the instructions in Section 8.4 should be followed.

7.2.2.1 Physical examination

A complete physical examination will include the examination of general appearance, skin, neck (including thyroid), eyes, ears, nose, throat, lungs, heart, abdomen, back, lymph nodes, extremities, vascular and neurological. If indicated based on medical history and/or symptoms, rectal, external genitalia, breast, and pelvic exams will be performed. Information about the physical examination must be present in the source documentation at the study site. Physical examination is to be performed according to the visit schedule as outlined in Table 7-1.

Significant findings that were present prior to the signing of informed consent must be included in the Medical History page on the patient's eCRF. Significant new findings that begin or worsen after informed consent must be recorded on the Adverse Event page of the patient's eCRF.

7.2.2.2 Vital signs

Vital signs include blood pressure (supine position preferred when ECG is collected), pulse measurement, and body temperature.

7.2.2.3 Height and weight

Height will be measured at screening.

Body weight (in indoor clothing, but without shoes) will be measured at screening and at subsequent time points as specified in Table 7-1.

7.2.2.4 Performance status

ECOG Performance status scale will be used as described in the Table 7-4.

Table 7-4ECOG performance status

Grade	ECOG status
0	Fully active, able to carry on all pre-disease performance without restriction
1	Restricted in physically strenuous activity but ambulatory and able to carry out work of a light or sedentary nature e.g., light house work office work
	sedemary nature e.g., light house work, once work

Grade	ECOG status
2	Ambulatory and capable of all self-care but unable to carry out any work activities. Up and about more than 50% of waking hours
3	Capable of only limited self-care, confined to bed or chair more than 50% of waking hours
4	Completely disabled. Cannot carry on any self-care. Totally confined to bed or chair
5	Dead

7.2.2.5 Laboratory evaluations

Local site laboratories will be used for the analysis of scheduled hematology, biochemistry, and other blood specimens collected as part of safety monitoring. All unscheduled blood testing will also be performed locally. The time windows granted for laboratory evaluations are identical to the corresponding visit time windows for each visit (refer to Section 7.1).

Laboratory abnormalities that are considered clinically significant, induce clinical signs or symptoms, require concomitant therapy or require dose adjustments in ribociclib treatment (see Section 8.1) constitute an adverse event (AE) and must be reported as an AE on the AE eCRF page.

Laboratory values obtained at the screening visit will be used to assess eligibility to meet Inclusion criteria. If patient meets all inclusion and no exclusion criteria, the screening labs can be used for baseline if patient is dosed within 14 days of the screening visit. If patient cannot be dosed within 14 days of screening, then the labs should be repeated the day before patient starts dosing (see baseline visit in Table 7-1).

Only selected laboratory parameters (see Table 7-5) will be collected on the eCRF.

Test Category	Test Name			
Hematology	WBC, ANC,	WBC, ANC, absolute lymphocyte count, hemoglobin, platelets		
Chemistry	Screening	ALT (SGPT), AST (SGOT), calcium corrected for serum albumin, creatinine c creatinine clearance, potassium, sodium, magnesium, total bilirubin (or direct bilirubin if Gilbert's syndrome)		
	Scheduled visits	Alkaline phosphatase, ALT (SGPT), AST (SGOT), total bilirubin, direct bilirubin (if clinically indicated)		
		Note: potassium, sodium, calcium corrected for serum albumin, and magnesium are to be monitored but are not captured in the eCRF. Abnormal electrolyte lab results should be reported as AEs at the investigator's discretion.		
Coagulation	International normalized ratio [INR]			
Pregnancy	Serum and Urine			

 Table 7-5
 Local Clinical laboratory parameters collection plan

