1.2.1.1 Non-clinical data

Ribociclib inhibits the phosphorylation of Rb at CDK4/6-binding sites with an average IC50 of 60 nM in Jeko-1 MCL cells that overexpress cyclin D1. Regardless of the various genetic aberrations that may be present in the cancer cells, the anti-tumor activity of ribociclib requires the presence of functional pRb.

Cardiac safety studies *in vivo* demonstrated QT prolongation with the potential to induce premature ventricular contractions (PVCs) at higher exposure levels. The effects of ribociclib on the bone marrow (hypocellularity), lymphoid system (lymphoid depletion), intestinal mucosa (atrophy), the kidney (concurrent degeneration and regeneration of tubular epithelial

cells), skin (atrophy), bone (decreased bone formation) and testes (atrophy) are considered to be related to the pharmacological inhibition of cell replication in these tissues due to CDK4/6 inhibition. The hepatobiliary system (proliferative changes, cholestasis, sand-like gallbladder calculi and inspissated bile) was identified as an additional target organs of toxicity that are not likely related to the primary pharmacology of ribociclib. Generally, all these effects of ribociclib demonstrated either reversibility or a clear trend towards reversibility. Ribociclib did not show an indication for a genotoxic potential. Reproductive studies in animals have demonstrated that ribociclib is embryotoxic, fetotoxic and teratogenic.

In vitro, ribociclib was a reversible inhibitor of human cytochrome P450 (CYP) enzymes CYP1A2, CYP2E1 and CYP3A4 and a time-dependent inhibitor of CYP3A4. Under therapeutic conditions, inhibition of CYP3A4 is likely to occur, while inhibition of CYP1A2 or CYP2E1 is not expected. The *in vitro* inhibitory potency of ribociclib for the transporters breast cancer resistance protein (BCRP), organic cation transporter 2 (OCT2), multidrug and toxin extrusion protein-1 (MATE1), and bile salt export pump (BSEP) may translate into clinically relevant inhibition at therapeutic doses.

Elimination of ribociclib is dominated by oxidative metabolism mainly via CYP3A4 with a minor contribution by flavin-containing monooxygenase 3 (FMO3). Although ribociclib is a substrate of the P-glycoprotein (P-gp) efflux transporter, this process is likely not clinically relevant due to the high passive permeability of ribociclib.

Refer to the most recent ribociclib [Investigator's Brochure] for additional details.

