1.2.1.2.1 Clinical safety of ribociclib

Clinical safety of ribociclib with endocrine agents such as letrozole, tamoxifen, exemestane and fulvestrant has been evaluated in several phase I and III combination trials. The recommended dose of ribociclib in combination with these agents was declared as 600 mg qd on a 3 weeks on/1 week off schedule.

The safety profile of ribociclib in combination with letrozole was investigated in a randomized clinical trial of ribociclib and letrozole versus placebo and letrozole (CLEE011A2301) in 668 treatment-naive postmenopausal women with HR-positive, HER2-negative, advanced BC. Most common treatment-emergent AEs reported in the ribociclib arm in this study occurring in >30% of patients were neutropenia (74.3%), nausea (51.5%), infections (50.3%), fatigue (36.5%), diarrhea (35.0%), alopecia (33.2%) and leukopenia (32.9%). The most common grade 3 or 4 AEs reported in \geq 5 % of patients in the ribociclib arm were neutropenia (59.3%), leukopenia (21.6%), hypertension (9.9%), increased alanine aminotransferase (9.3%), lymphopenia (6.9%) and increased aspartate aminotransferase (5.7%). Febrile neutropenia occurred in 1.5% of the patients in the ribociclib arm. Blood creatinine increases were reported in 6.9% of patients. Four patients (1.2%) met the biochemical and clinical criteria for Hy's Law with 3 reported as treatment-related and all 4 returning to normal values after treatment

discontinuation. Eleven patients (3.3%) presented on treatment QTcF prolongation >480 msec. Serious AEs were reported in 21.3% of patients in the ribociclib arm with 7.5% of serious AEs deemed by investigators as treatment-related. There were 3 fatal events in the ribociclib arm (disease progression, sudden death, unknown cause) with 1 AE (sudden death) reported as treatment-related in a patient that had grade 3 hypokalemia and grade 2 QTcF prolongation (483 msec). Neutropenia, QT interval prolongation and hepatobiliary toxicity are considered to be important identified risks for ribociclib which appear to be manageable and reversible with adequate monitoring, interruption and/or reduction of ribociclib dosing.

For a comprehensive review of safety profile of ribociclib in combination with endocrine agents refer to the most recent ribociclib [Investigator's Brochure].

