7.1 Study flow and visit schedule

Table 7-1 lists all of the assessments and indicates with an "X", the visits when they are performed. All data obtained from these assessments must be supported in the patient's source documentation. The table indicates which assessments produce data to be entered into the clinical database (D) or remain in source documents only (S) ("Category" column).

Note:

- During screening visits, lab assessments including white blood cell (WBC) count, absolute neutrophil count (ANC), absolute lymphocyte count, hemoglobin, platelets, INR, ALT, AST, total bilirubin (or direct bilirubin if Gilbert's Syndrome), serum creatinine, electrolytes (potassium, sodium, calcium corrected for serum albumin, and magnesium) are required to be collected within 14 days of C1D1 for eligibility assessment.
- During treatment phase, only selected labs assessments are required to be collected in the clinical database at the patient scheduled visits: WBC, ANC, absolute lymphocyte count,

hemoglobin, platelets, AST, ALT, ALP, total bilirubin, and direct bilirubin (if clinically indicated). Electrolytes should be monitored at the beginning of each cycle before resuming ribociclib dose during the first 6 cycles and as clinically indicated thereafter. The results should not be captured in clinical database. Eventual abnormal electrolyte lab results should be reported as AEs at the investigator's discretion.

- ECG will be performed at screening (within 5 days of C1D1), C1D15, C2D1, then as clinically indicated, and EOT.
- If treatment is withheld at any time during the study, all study visits, safety assessments, and efficacy assessments should be adjusted accordingly to match the treatment cycles.
- For all visits, there is a +/-3 day window on assessments to take into account scheduling over public holidays, if not explicitly specified otherwise.

Novartis	
Amended Protocol Version 04 (Clean)	

Confidential

Table 7-1	Visit evaluation	schedule	(Core Phase)
-----------	------------------	----------	-------------	---

	Category	Reference to Protocol Section	Screening Phase	Core	Core Treatment Phase						End of study treatment (EOT) within 7 days from the last dose of study treatment	Safety follow up within 30 days of last dose of study treatment		
Visit name			Screening (-28 Days to Day 1)	C1D1	C1D15	C2D1	C2D15	C3D1	C4D1	C5D1	C6D1-C11D1	C12D1 and subsequent cycles (up to cycle 36)		
Screening														
Study Informed Consent	D	7	×											

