10.8 Sample size calculation

A sample size of 3,000 patients is planned to be enrolled in this study to detect rare AEs (frequency ~0.1%) with high probability. This will allow for a greater precision when reporting rare, but clinically meaningful AEs (e.g. febrile neutropenia, QT prolongation, renal insufficiency, thromboembolic events, etc.). For example, if the rate of an AE is 0.1%, then the probability of observing at least 1 AEs out of 3000 patients is 95.0%. A sample size of 3,000 patients will allow for a meaningful safety analysis of specific patient subgroup of particular interest. For example, the expected size of male patients may be 30 (~ 0.1% of total population), patients with ECOG PS=2 may be 150 (~5% of total population), and patients with one prior line of chemotherapy may be 300 (~10% of total population). Table 10-1 below provides a 95% confidence interval (CI) and the corresponding width of the 95% CI, with different rates of rare AEs observed in [LEE011A2301] study) for overall population as well as for subgroups of various sizes.

Number of Patients	Number of AE	Rate	Lower 95% Cl	Upper 95% Cl	Width*
QT prolongatio	n (observed rate =	3.5%)			
30	1	0.0333	0.0008	0.1722	0.1713
150	5	0.0333	0.0109	0.0761	0.0652
300	10	0.0333	0.0161	0.0604	0.0443
3000	99	0.0330	0.0269	0.0400	0.0131
Febrile neutrop	enia (observed rat	e = 1.5%)			
30	0	0	0	0.1157	0.1157
150	3	0.020	0.0041	0.0573	0.0532
300	5	0.0167	0.0054	0.0385	0.0330
3000	45	0.0150	0.0110	0.0200	0.0091

Table 10-1 Confidence Intervals associated with AEs of interest for subgroups

Renal insufficiency / creatinine increase (observed rate = 0.5%)					
30	0	0	0	0.1157	0.1157
150	1	0.0067	0.0002	0.0366	0.0364
300	2	0.0067	0.0008	0.0239	0.0231
3000	15	0.0050	0.0028	0.0082	0.0054

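### No on-treatment serum creatinine is scheduled or captured, yet Section 10.8 and Table 10-1 claim precision for renal insufficiency/creatinine increase; that interval reflects sampling error only and the rate is likely biased low

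*Protocol*

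**What the plan says.** **Laboratory plan.** Protocol Table 7-5 (Section 7.2.2.5) puts creatinine or creatinine clearance in the screening chemistry row. The scheduled-visit row reads "Alkaline phosphatase, ALT (SGPT), AST (SGOT), total bilirubin, direct bilirubin (if clinically indicated"). Section 7.1 draws the same line: serum creatinine is in the list required for eligibility, whereas during treatment "only selected labs assessments are required to be collected in the clinical database at the patient scheduled visits: WBC, ANC, absolute lymphocyte count", then hemoglobin, platelets, AST, ALT, ALP and bilirubin. Both places add that potassium, sodium, corrected calcium and magnesium (7.1 simply says electrolytes) are monitored without being entered on the eCRF. Creatinine is not among them. Table 7-1 schedules chemistry from C1D15 to C6D1 and at end of treatment, and refers to Table 7-5 for its content.

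**Precision claim.** Section 10.8 states: "A sample size of 3,000 patients is planned to be enrolled in this study to detect rare AEs (frequency ~0.1%) with high probability". It says this gives greater precision for "rare, but clinically meaningful AEs (e.g. febrile neutropenia, QT prolongation, renal insufficiency, thromboembolic events, etc".). Table 10-1 has three blocks; the third is headed "Renal insufficiency / creatinine increase (observed rate = 0.5"%), with 15 events in 3,000 patients.

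**Background.** Section 1.2.1.2.1 says of the ribociclib-letrozole phase III trial (CLEE011A2301): "Blood creatinine increases were reported in 6.9% of patients". Section 1.2.1.1 lists among the animal findings "the kidney (concurrent degeneration and regeneration of tubular epithelial" cells), and says inhibition of the transporters OCT2 and MATE1 may be clinically relevant.

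**The concern.** A creatinine increase is defined by a laboratory value, so it cannot be found unless someone draws the sample. The other two events in Table 10-1 have scheduled on-treatment measurements behind them: ECGs at C1D15, C2D1 and end of treatment for QT prolongation, and neutrophil counts through Cycle 6 and at end of treatment for febrile neutropenia. The renal block has none.

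The consequence is one of ascertainment. A Clopper-Pearson interval treats every qualifying case as counted. If some go undetected, the interval is centred too low and its stated precision is misleading. SAP 2.8.4 plans worst-grade and baseline-shift tables for biochemistry; for creatinine these would have a baseline but no scheduled post-baseline value. The protocol's own background gives reasons to want that value.

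**Working it through.** **Inputs from the documents.** N = 3,000; renal rate 0.5% (Section 10.8, Table 10-1); creatinine increase 6.9% (Section 1.2.1.2.1); two-sided 95% intervals.

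**Input that is assumed.** s, the fraction of patients with a qualifying renal/creatinine adverse event who are actually identified. The documents give no value; s = 0.8, 0.75 and 0.5 are shown.

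**Step 1: the plan's own figures.** Section 10.8 says: "if the rate of an AE is 0.1%, then the probability of observing at least 1 AEs out of 3000 patients is 95.0"%. Check: 1 − (1 − 0.001)^3000 = 0.9503, which agrees. Exact Clopper-Pearson intervals for the renal block:

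| Events / N | Lower | Upper | Width |
|---|---|---|---|
| 0 / 30 | 0 | 0.1157 | 0.1157 |
| 1 / 150 | 0.0002 | 0.0366 | 0.0364 |
| 2 / 300 | 0.0008 | 0.0239 | 0.0231 |
| 15 / 3000 | 0.0028 | 0.0082 | 0.0054 |

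All four rows match Table 10-1. The arithmetic is not at fault.

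**Step 2: coverage under incomplete detection.** If the true rate is p, the observed count is Binomial(3000, s·p). Coverage is the probability that the interval computed from that count contains p. For p = 0.5% the interval contains p when the count is 8 to 23; for p = 6.9%, when it is 180 to 235.

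| True rate p | s | Expected count | Observed rate | Coverage of p |
|---|---|---|---|---|
| 0.5% | 1 | 15 | 0.50% | 96.3% |
| 0.5% | 0.8 | 12 | 0.40% | 90.9% |
| 0.5% | 0.75 | 11.25 | 0.375% | 87.2% |
| 0.5% | 0.5 | 7.5 | 0.25% | 47.5% |
| 6.9% | 1 | 207 | 6.90% | 95.6% |
| 6.9% | 0.8 | 165.6 | 5.52% | 13.4% |
| 6.9% | 0.75 | 155.25 | 5.175% | 2.5% |
| 6.9% | 0.5 | 103.5 | 3.45% | below 0.1% |

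**Step 3: shortfall against precision.** At 0.5%, s of 0.8 to 0.5 loses 0.10 to 0.25 point, against a half-width of 0.54/2 = 0.27 point. At 6.9% the loss is 6.9 − 5.52 = 1.38 to 6.9 − 3.45 = 3.45 points, against a half-width of about 1.96 × √(0.069 × 0.931/3000) = 0.9 point.

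**Step 4: the two rates.** Section 10.8 takes its table rates from LEE011A2301, and Section 1.2.1.2.1 reports the 6.9% from the same trial. On 3,000 patients they imply 15 and 207 cases. Event definition or grade may differ, but the protocol does not say so.

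**The case against.** Several points on the other side are sound.

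- **Laboratory value versus adverse event.** The primary endpoint is reported adverse events. Under Section 8.1.1 an abnormal result counts only if it causes symptoms, is judged clinically significant, or needs therapy or a change in study medication. Many silent rises would not qualify even if measured. Symptomatic or diagnosed renal insufficiency, and anything found on local testing that qualifies, still reaches the adverse event page. The loss is confined mainly to asymptomatic rises that an investigator would have judged significant.
- **A targeted panel.** The events of special interest are neutropenia, QT prolongation and hepatobiliary events, and the scheduled tests match them. That explains the omission, but not why the renal event carries a precision claim.
- **SAP 2.8.4.** It summarises whatever assessments are available and does not name creatinine, so it is not contradicted.

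A reader might also infer four stronger things that the documents do not support:

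- *Creatinine is measured only once, at screening.* Table 7-5 is a collection plan. Section 7.2.2.5 calls for repeat labs the day before dosing if dosing falls more than 14 days after screening, and sites may test locally at any time. What is absent is scheduled or captured on-treatment creatinine.
- *The trial was sized on this event.* Renal insufficiency is one example in a list, and SAP Section 3 says the size does not rest on statistical considerations.
- *The interval would miss the truth.* At 0.5% it would still cover about 91% of the time with 80% detection. Near-certain exclusion needs the 6.9% rate or very poor detection.
- *The bias differs by country or site.* This is possible where testing is discretionary, but the documents contain nothing that shows it.

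**Conclusion.** The point holds as a gap between the precision claim and data collection. Two sections agree that creatinine is scheduled before treatment only, and the list of analytes monitored without capture does not include it. Table 10-1's renal interval is therefore right about sampling error and silent about missed cases. The reported rate is likely to be low by an amount the trial cannot estimate.

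The size depends on two unknowns: the detection fraction, which is assumed throughout, and which of the protocol's two rates applies. At 0.5% the damage is modest if detection is good and serious if half the cases are missed. At 6.9% the interval is unreliable at 80% detection or below. The likely downward direction does not depend on either choice. This is worth correcting, but it does not call the main safety results into question.

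**What to change.** **In the design (this protocol as a template, or any similar study).** Add serum creatinine to the scheduled-visit row of Table 7-5 and to the treatment-phase list in Section 7.1, run it on the chemistry sample already drawn, enter it on the eCRF, and include it in the SAP 2.8.4 grade and shift tables. The cost is one routine analyte and one eCRF field per chemistry visit.

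**For this trial.** Amendment 04 records the last Core Phase visit as 08-Nov-2019, and the Extension schedule (Table 7-2) has no chemistry, so adding the analyte now yields no data. What can still be done is wording only:

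1. Remove the renal event from the precision statement in Section 10.8 and from Table 10-1, or qualify it as covering sampling error alone.
2. Footnote the reported renal/creatinine adverse event rate as resting on unscheduled testing and clinical diagnosis, and so a likely underestimate.
3. State the event definition and grade behind the 0.5% and the 6.9%, and reconcile the two.
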